6.4 Concomitant Medications (Including Over-the-counter Drugs)

The following information about concomitant medications and drugs used to treat adverse events from the time of informed consent (Visit 0) to the examination at completion of study treatment or the examination at discontinuation^{†††}: whether drugs were used, drug names, duration of treatment, and reason for use. If prohibited concomitant medications, intravenous antiarrhythmic drugs, P-glycoprotein (P-gp) inhibitors, or acidic NSAIDs were administered, the dose and route will also be entered on case report forms in addition to the above.

In the duration of follow-up during study drug interruption and after study drug discontinuation, whether the following drugs have been used will be surveyed at least every 8 weeks, and if they have, the same information will be surveyed as in the case where drugs such as prohibited concomitant medications were used, and entered on the case report form.

 Anticoagulants, thrombolytic drugs, antiplatelet drugs, intravenous antiarrhythmic drugs, acidic NSAIDs

^{†††:} For subjects withdrawn from study treatment and subjects withdrawn from study participation

Testing drugs, fluid infusions, fluid supplementation, nutritional formulations, disinfectants, and anesthetics, other than those used for treating adverse events, will not be entered on case report forms.

6.5 Head Imaging

In the eligibility assessment examination, head imaging (computed tomography [CT] and magnetic resonance imaging [MRI]) will be performed. It will be confirmed that there are no findings of active bleeding, and the imaging method, date of imaging, and bleeding findings will be entered on case report forms. However, if imaging is performed within the 4 weeks from the day of informed consent as part of routine care, the results of this imaging may be used to quality the subject, with the subject's consent.

6.6 Twelve-lead Electrocardiogram

Twelve-lead electrocardiography (ECG) will be performed at the eligibility assessment examination, during the study treatment period (once every 12 weeks from Week 4 to Week 48 [Visit 4, Visit 7, Visit 10, and Visit 13], and once every 24 weeks from Week 48 onward [Visit 16, Visit 19, Visit 22...]), at the examination at completion of study treatment, and at the final follow-up examination or the examination at discontinuation and the date of examination, whether AF was present, and other findings will be entered on case report forms. If any clinically meaningful change compared with the results of the eligibility assessment examination is observed in examinations after the initiation of study treatment, the investigator or subinvestigator will assess whether to handle this change as an adverse event, and if it is considered to be an adverse event, it will be entered in the adverse event field of the case report form.

6.7 Vital Signs

6.7.1 Height

Height will be measured at the eligibility assessment examination, and the date of measurement and results will be entered on case report forms. Body mass index (BMI) will also be calculated using the body weight measured at the eligibility assessment examination.

^{†††:} For subjects withdrawn from study treatment and subjects withdrawn from study participation

6.7.2 Body Weight

Body weight will be measured at the eligibility assessment examination, all visits during the study treatment period, the examination at completion of study treatment, and the final follow-up examination or the examination at discontinuation the date of measurement and results will be entered on case report forms. If any significant change compared with the eligibility assessment examination is observed in examinations after the initiation of study treatment, the investigator or subinvestigator will assess whether to handle this change as an adverse event, and if it is considered to be an adverse event, it will be entered in the adverse event field of the case report form.

6.7.3 Blood Pressure/Pulse Rate

Systolic blood pressure, diastolic blood pressure, and pulse rate will be measured at the eligibility assessment examination, all visits during the study treatment period, the examination at completion of study treatment, and the final follow-up examination or the examination at discontinuation^{‡‡‡}, and the date of measurement and results will be entered on case report forms.

If the subject makes visits during study drug interruption or after study drug discontinuation, systolic blood pressure, diastolic blood pressure, and pulse rate will be measured at least every 8 weeks, and the dates of measurements and results will be entered on the case report form.

If any significant change compared with the eligibility assessment examination is observed in tests after the initiation of study treatment, the investigator or subinvestigator will assess whether to handle this change as an adverse event, and if it is considered to be an adverse event, it will be entered in the adverse event field of the case report form. During study treatment, if systolic blood pressure persistently exceeds 160 mmHg or diastolic blood pressure persistently exceeds 100 mmHg on the same day, study treatment for the relevant subject will be promptly interrupted. After treatment is interrupted, repeat measurements will be made at least one week apart, to consider whether study treatment can be resumed (see "4.2.1.1 Interruption and Resumption of Study Drug").

6.8 Laboratory Tests

Blood samples and urine samples for laboratory tests will be collected at the eligibility assessment examination, once every 8 weeks during the study treatment period (from Week 4 to Week 48, at Visit 3, Visit 5, Visit 7, Visit 9, Visit 11, and Visit 13/from Week 48 onward, at Visit 14, Visit 15, Visit 16...), the examination at completion of study

treatment, and the final follow-up examination or the examination at discontinuation. §§§
All laboratory tests will be performed as a batch by SRL, Inc.

- 1) Hematology test
 - Red blood cell count, hemoglobin, hematocrit, white blood cell count, white blood cell differentials (neutrophils, lymphocytes, monocytes, eosinophils, and basophils), platelet count, and PT-INR*
 - *: PT-INR will be measured if the subject received warfarin within the 8 weeks prior to the day of informed consent, or if the subject is receiving warfarin during study drug interruption or during the follow-up after study drug discontinuation.
- 2) Blood chemistry test
 - Total protein, albumin, total bilirubin, direct and indirect bilirubin, ** AST, ALT, ALP, GGT, LDH, CK, BUN, creatinine, uric acid, Na, K, Cl, total cholesterol, triglyceride **: Direct and indirect assays will be performed when total bilirubin ≥ 2 mg/dL
- Endocrinology tests
 Troponin I, human brain natriuretic peptide (BNP)
- 4) Urinalysis

Urine glucose, urine protein, urine blood, urinary sediment (red blood cells)

If the subject makes visits during study drug interruption or after study drug
discontinuation, measurement of laboratory test items the investigator or subinvestigator
considers suitable (if warfarin is being administered, PT-INR is mandatory) will be
requested, and the dates when specimens were collected will be entered on case report
forms.

If any abnormal laboratory data (deviations from reference ranges) are observed, the investigator or subinvestigator will assess whether to handle these data as an adverse event, and if they are considered to be adverse events, they will be entered in the adverse event field of the case report form.

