ATTACHMENT	82
APPENDICES	83
LIST OF IN-TEXT TABLES	
Table of Study Procedure and Specimen Collection Schedule	6
Table 6-1 Study Procedure and Specimen Collection Schedule	34
Table 6-2 Times of Blood Sampling for Measuring Plasma Drug Concentration	41
Table 9-1 Information to Be Reported When an Adverse Event Occurs	51
Table 15.9-1 The EDC System	68
LIST OF IN-TEXT FIGURES	
Figure 3-1 Study Design	18
Figure 4.1-1 Enrollment Procedure for Subjects	23

LIST OF ABBREVIATIONS AND DEFINITION OF TERMS

List of Abbreviations

Abbreviation	Definition				
AF	atrial fibrillation				
ALP	alkaline phosphatase				
ALT	L-alanine aminotransferase				
aPTT	activated partial thromboplastin time				
AST	L-aspartate aminotransferase				
BMI	body mass index				
BNP	brain natriuretic peptide				
BUN	blood urea nitrogen				
CK	creatine kinase				
CLcr	creatinine clearance				
CT	computed tomography				
CV	cardiovascular				
DVT	deep vein thrombosis				
ECG	electrocardiogram				
EDC	electronic data capture				
F1+2	prothrombin fragment 1+2				
GCP	good clinical practice				
GGT	gamma glutamyl transferase				
ICH	International Council for Harmonisation of Technical Requirements for Pharmaceuticals for Human Use				
INR	international normalized ratio				
IRB	institutional review board				
IRT	interactive response technology				
ITT	Intent-to-treat				
IWRS	interactive web response system				
LC-MS/MS	liquid chromatography tandem mass spectrometry				
LDH	lactic acid (lactate) dehydrogenase				
MACE	major adverse cardiovascular event				
MedDRA	Medical Dictionary for Regulatory Activities				
MI	myocardial infarction				
mITT	Modified intent-to-treat				
MRI	magnetic resonance imaging				
NSAIDs	non-steroidal anti-inflammatory drugs				
NVAF	non-valvular atrial fibrillation				
NYHA	New York Heart Association				
PD	pharmacodynamics				
P-gp	P-glycoprotein				
PGx	pharmacogenomics				

PK	pharmacokinetics
PPS	per protocol set
PT	prothrombin time
PTE	pulmonary thromboembolism
PT-INR	prothrombin time expressed as international normalized ratio
SEE	systemic embolic event
TEAE	treatment-emergent adverse event
TIA	transient ischemic attack
VKA	vitamin K antagonist
VTE	venous thromboembolic event
Xa	activated coagulation factor X

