5.3.2 Prohibited Tests

To ensure blinding, tests affecting blinding will be prohibited at the study site from the initiation of study treatment until 2 days after the day of the examination at completion of study treatment (excluding the duration of follow-up at least 3 days after the date of study drug discontinuation or the date of study drug interruption) or the final follow-up examination (when the study treatment is continued after the examination at completion of study treatment), such as the following: pharmacodynamic (PD) indicator tests (prothrombin time [PT], activated partial thromboplastin time [aPTT]), and biomarker tests (D-dimer, prothrombin fragment 1+2 [F1+2], activated coagulation factor X [Xa]). However, cases where testing is unavoidable, for example to treat an adverse event or in an emergency, will be permitted. Whether PD and biomarker tests were performed during the period from the initiation of study treatment to the day of the examination at completion of study treatment, the date of conduction of these tests, and the concerned test items will be recorded on case report forms.

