6.12.2.4 Measurement of Pharmacodynamic Indicators and Biomarkers

Centralized measurement of PD indicators and biomarkers will be performed at SRL, Inc. SRL, Inc. will measure PD indicators (PT and aPTT) and biomarkers (D-dimer and F1+2) promptly after receiving specimens. The results of measurement will not be disclosed to the study site or the Sponsor, except in cases where this is unavoidable, such as when action is taken to treat adverse events or in emergencies.

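### As worded, the section 6.8 footnote can be read to require on-treatment PT-INR in recent warfarin users, and no stated rule withholds those results

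*Combined protocol and SAP*

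**What the plan says.** Section 6.8 (Laboratory Tests) lists PT-INR in the hematology test. Samples are taken at eligibility, "once every 8 weeks during the study treatment period", at completion, and at the final follow-up or discontinuation examination. Measurement is central: "All laboratory tests will be performed as a batch by SRL, Inc".

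The PT-INR footnote has two triggers joined by *or*:

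- Trigger 1: "PT-INR will be measured if the subject received warfarin within the 8 weeks prior to the day of informed consent".
- Trigger 2: "or if the subject is receiving warfarin during study drug interruption or during the follow-up after study drug discontinuation".

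The same section asks the investigator to judge out-of-range laboratory values as possible adverse events. It makes no exception for PT-INR.

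Two other sections deal with tests that could reveal treatment:

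- Section 5.3.2 (Prohibited Tests) states that "tests affecting blinding will be prohibited at the study site from the initiation of study treatment" and names PT and aPTT among them. Follow-up from 3 days after the study drug stops is exempt.
- Section 6.12.2.4 states, for the centrally measured PT, aPTT, D-dimer and F1+2, "The results of measurement will not be disclosed to the study site or the Sponsor", except where adverse event treatment or an emergency makes it unavoidable. Those samples are taken at Visit 1 and Visit 3 only (6.12.2.1 and 6.12.2.2).

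The List of Abbreviations defines PT-INR as "prothrombin time expressed as international normalized ratio".

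**The concern.** Trigger 2 is confined to time off study drug. Trigger 1 is a baseline fact with no visit attached. Once met, it applies at every scheduled hematology draw, including those on blinded study drug. PT-INR carries the same information as PT, which the protocol itself regards as a threat to blinding. Yet the rule that keeps PT from site and Sponsor does not extend to the section 6.8 panel.

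On-treatment PT-INR also has no stated purpose. Section 5.3.1 prohibits anticoagulants from consent to the last dose except during off-drug follow-up, and trigger 2 already covers warfarin in that period.

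A treatment clue could act in three places:

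- **Interruption.** This is partly at the investigator's discretion (4.2.1.1), and a physician-instructed interruption is one of the things that makes a bleed clinically relevant non-major (9.1.2).
- **Reporting.** Investigators report the events that the committees then assess (6.14, 6.15).
- **Sponsor decisions.** Analysis sets, data handling and possible extra covariates are settled before unblinding (11.2, 11.3, 11.4.2.1.1).

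**Working it through.** The plan states no figure of its own on this point. The check sets the provisions side by side, then counts draws and works out who could be affected.

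**1. Scope of the masking**

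| | PT (6.12.2) | PT-INR (6.8, trigger 1) |
|---|---|---|
| Measured | centrally | centrally |
| On-treatment visits | Visit 3 | every 8-weekly hematology visit, read literally |
| Non-disclosure rule | yes (6.12.2.4) | none stated |
| Review by investigator | no | abnormal values are judged as possible adverse events |

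So at Visit 3, as written, a subject's PT is withheld while the same subject's PT-INR is not.

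**2. On-treatment draws per affected subject**

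Inputs: hematology at Visits 3, 5, 7, 9, 11 and 13, then every visit from Visit 14 (6.8). Visits are 4 weeks apart to Week 48 and 8 weeks apart after that (Table 6-1). The planned mean treatment duration is 2 to 2.5 years (5.2.1).

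- To Week 48: weeks 8, 16, 24, 32, 40, 48 = 6 draws.
- To 2 years (Week 104, Visit 20): 6 + (104 − 48)/8 = 6 + 7 = 13.
- To 2.5 years (about Week 130; last draw at Week 128, Visit 23): 6 + (128 − 48)/8 = 6 + 10 = 16.

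These counts assume uninterrupted treatment. They leave out the eligibility, completion and final examinations.

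**3. Who meets trigger 1 and can still be randomized**

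Let *d* be the days from last warfarin to consent and *g* the days from consent to randomization. Trigger 1 needs *d* ≤ 56. Exclusion 2 in section 4.1.2 bars warfarin in the 8 weeks before randomization, so entry needs *d* + *g* > 56. Sections 3 and 4.1.3.1 allow up to 30 days after consent for eligibility assessment; I take 30 days as the longest gap to randomization.

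| Gap *g* (days) | Last warfarin before consent, *d* (days) |
|---|---|
| 0 | none |
| 7 | 50 to 56 |
| 14 | 43 to 56 |
| 21 | 36 to 56 |
| 30 | 27 to 56 |

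Under the body text the group is therefore narrow, but not empty unless randomization falls on the day of consent.

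Exclusion 2 in the synopsis omits warfarin. Exclusion 3 and the section 3 rationale both describe subjects receiving warfarin with INR below 1.6. On that wording the 8-week limit drops out and the group could be larger. These passages conflict and must be reconciled; the size of the affected group depends on the outcome.

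**4. What cannot be computed**

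The documents give no count of recent warfarin users and no figure for the PT or PT-INR shift on 15 mg. Section 6.8 also fixes no draw time relative to the dose. The degree of unblinding therefore has no calculable value.

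**The case against.** The best case for the plan is that only eligibility testing was meant. Elsewhere PT-INR appears in just two settings: at baseline in prior warfarin users (6.2), and off study drug while warfarin is taken (4.2.1.2, 4.2.2.2). The two triggers match these settings. Exclusion 3 needs INR from three examinations at least 4 weeks apart, including the eligibility one. That spans at least 8 weeks, which would explain the look-back in trigger 1. This reading is plausible and may well be the intent, but the footnote does not say it, and a laboratory following the text would test at every panel.

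A reader might infer that the plan breaks its own section 5.3.2. It does not: the prohibition applies to tests at the study site, and PT-INR is measured centrally.

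A reader might also infer that sites and the Sponsor will see these results. That is not established. Section 15.9 leaves the method for preparing measurement reports to be specified elsewhere, and a laboratory procedure outside these documents may mask them. What stands is that no rule in these documents does so, while the abnormal-value paragraph in 6.8 presupposes that panel results reach the investigator.

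Finally, independent committees make the final assessment of efficacy and bleeding events (7, 9.1) under blinded conditions (3). That limits the effect on event classification. It does not protect which events investigators report or when they interrupt study drug.

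**Conclusion.** The point holds as a gap in wording and masking, of minor priority. Read literally, trigger 1 yields 13 to 16 on-treatment PT-INR results per affected subject over 2 to 2.5 years, against one on-treatment visit at which PT is covered by a non-disclosure rule. Under the body version of exclusion 2 the affected group is small; under the synopsis version it could be larger.

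It would be tempting to assume a share of recent warfarin users and convert it into numbers of subjects and primary events. The documents give no basis for such a share, and a large one sits badly with the body exclusion. They do not support a claim that the primary comparison is materially unblinded or biased.

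The conclusion rests on the literal reading of the footnote, on a longest gap of 30 days from consent to randomization, and on the protocol's own position that PT affects blinding. PT-INR in subjects taking warfarin off study drug is not in question.

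**What to change.** Limit the first trigger in the section 6.8 footnote to the eligibility assessment examination, and leave the second trigger as it is. If on-treatment PT-INR is wanted after all, state why and extend the 6.12.2.4 non-disclosure rule, with its emergency exception, to PT-INR measured on study drug.

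Separately, reconcile the synopsis and body versions of exclusion 2 with exclusion 3 and the section 3 rationale, so that it is clear which subjects the trigger can reach.

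The cost of the footnote change is one edited sentence or one central laboratory reporting setting. No planned efficacy analysis uses on-treatment PT-INR, and monitoring of warfarin taken off study drug is unaffected.

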6.9 Creatinine Clearance

CLcr will be calculated using the Cockcroft-Gault formula at the eligibility assessment examination, once every 8 weeks during the study treatment period (from Week 4 to Week 48, at Visit 3, Visit 5, Visit 7, Visit 9, Visit 11, and Visit 13/from Week 48 onward, at Visit 14, Visit 15, Visit 16...), the examination at completion of study treatment, and the final follow-up examination or the examination at discontinuation,**** and entered on case report forms. If any significant change compared with the eligibility assessment

^{§§§:} For subjects withdrawn from study treatment and subjects withdrawn from study participation

examination is observed in CLcr after the initiation of study treatment, the investigator or subinvestigator will assess whether to handle this change as an adverse event, and if it is considered to be an adverse event, it will be entered in the adverse event field of the case report form.

Cockcroft-Gault formula

```
Males: \{(140 - age) \times body \text{ weight (kg)}\} \div \{72 \times serum \text{ creatinine (mg/dL)}\}\
Females: [\{(140 - age) \times body \text{ weight (kg)}\} \div \{72 \times serum \text{ creatinine (mg/dL)}\}] \times 0.85
```

6.10 Surgery

If a subject receives surgery between the initiation of study treatment and the examination at completion of study treatment or the examination at discontinuation,**** the investigator or subinvestigator will survey information relating to the surgery such as the date of surgery, reason for surgery, amount of blood lost during surgery, and whether blood transfusion was performed, and enter this on the case report form. If the surgery is due to an adverse event, the investigator or subinvestigator will perform a survey according to "9.4 Adverse Event Information to Be Reported" and enter information about the adverse event in the adverse event field of the case report form.

6.11 Hospitalization

If a subject is hospitalized between the initiation of study treatment and the examination at completion of study treatment or the examination at discontinuation,**** the investigator or subinvestigator will survey information relating to the hospitalization such as the date of hospitalization, the reason for hospitalization, and the date of discharge, and enter this on the case report form. If the hospitalization is due to an adverse event, the investigator or subinvestigator will perform a survey according to "9.4 Adverse Event Information to Be Reported" and enter information about the adverse event in the adverse event field of the case report form.

^{*****:} For subjects withdrawn from study treatment and subjects withdrawn from study participation

6.12 Plasma Drug Concentration, Pharmacokinetic Indicators, and Biomarkers

6.12.1 Plasma Drug Concentration

6.12.1.1 Blood Sampling Times and Meal Records for Measuring Plasma Drug Concentration

Blood sampling for measurement of plasma drug concentration will be performed on Week 8 (Visit 3) of the study treatment period (see Table 6-2). The investigator or subinvestigator will instruct the subject to make a visit without receiving the morning dose of the study drug, will collect a blood sample at the trough time promptly after the subject makes a visit, and will record the date of blood sampling and time of blood sampling on the case report form. The investigator or subinvestigator will also enter the times when the study drug was administered 2 days before and 1 day before the day of blood sampling, the start times of the meals before and after the study drug was administered on the day before blood sampling, and the start times of the meals before and after the study drug was administered on the day of blood sampling. After this, the subject will receive the study drug at the study site, and a blood sample will be collected 1 to 3 hours after the study drug was administered, and the time when the study drug was administered and the time when the blood sample was collected will be entered on the case report form. If possible, a blood sample will also be collected between 4 and 8 hours after the study drug was administered, and the time when the blood sample was collected will be entered on the case report form.

Table 6-2 Times of Blood Sampling for Measuring Plasma Drug Concentration

Time of blood sampling	Remarks
Trough	Must be collected
Between 1 to 3 hours after the study drug is administered	Must be collected
Between 4 to 8 hours after the study drug is administered	Will be collected if possible

6.12.1.2 Method of Blood Sampling for Measuring Plasma Drug Concentration, Plasma Isolation, and Storage

A quantity of 5 mL of venous blood will be collected using a 5 mL vacuum blood sampling tube containing lithium heparin. Directly after sampling, the blood will be mixed by inversion and cooled. The specimen will be promptly centrifuged for 10 minutes at $1500 \times g$. The plasma will be immediately fractionated into a container for submission, and stored at the study site at no higher than -20°C , protected from light

until it is collected by SRL, Inc. (the process from sampling of intravenous blood to storage will be performed within 1 hour). SRL, Inc. will place the set of specimens stored according to the Sponsor's instructions in a container with dry ice and send it to the drug concentration measurement laboratory (Q² Solutions).

